ClinicalTrials.gov ID: NCT03502330

Title: APX005M With Nivolumab and Cabiralizumab in Advanced Melanoma, Non-small Cell Lung Cancer or Renal Cell Carcinoma

Document Type: Protocol and SAP

Date: 3/21/2022

A Phase I/Ib Study of APX005M in Combination with Nivolumab and Cabiralizumab in Patients with Advanced Melanoma, Non-small Cell Lung Cancer or Renal Cell Carcinoma Whose Disease Has Progressed on Anti-PD-1/PD-L1 Therapy

BMS Protocol Number:	CA025-007
Institutional Protocol Number	HIC #2000021757
Investigational Products:	APX005M, Cabiralizumab (FPA008), and Nivolumab
IND Number:	139038
Development Phase:	Phase 1/1b
Indications Studied:	Melanoma, NSCLC, RCC
Protocol Version:	10
Date of Protocol:	21 Mar-2022
Sponsor:	Yale Cancer Center
Industry Collaborators:	Bristol-Myers Squibb, Apexigen, Inc.
Principal Investigator:	[name] Yale Cancer Center [contact] [contact]
Co-Principal Investigators	[name]

Confidentiality Statement

The information contained in this document is confidential and the proprietary property of Bristol-Myers Squibb and Apexigen. Any unauthorized use or disclosure of such information without the prior written authorization of Bristol-Myers Squibb and Apexigen is prohibited.

Study Synopsis

Title: A Phase 1/1b Study of APX005M in Combination with Nivolumab and Cabiralizumab in Patients with Advanced Melanoma, Non-small Cell Lung Cancer or Renal Cell Carcinoma Whose Disease Has Progressed on Anti-PD-1/PD-L1 Therapy

Protocol Number: CA025-007

Clinical Phase: 1/1b

Sponsor: Yale Cancer Center

Industry Collaborators: Bristol-Myers Squibb, Apexigen, Inc.

Study Center: Yale Cancer Center

Background: New combinatorial therapeutic strategies are needed to overcome resistance to immune checkpoint inhibitors in a number of malignancies. We hypothesize that manipulation of the innate immune system by targeting macrophage activity will assist in reversing local immune suppression and overcome resistance to PD-1/PD-L1 inhibition.

Objectives:

Phase 1 Objectives

Primary	
• To assess the safety and tolerability of APX005M in combination with cabiralizumab• To assess the safety and tolerability of APX005M in combination with cabiralizumab and nivolumab• To determine the recommended phase 2 dose (RP2D) of APX005M in combination with a fixed dose of cabiralizumab and nivolumab• To determine the adverse event (AE) profile of this combination
Secondary	
Exploratory	
• To characterize the pharmacokinetic (PK) profile of APX005M when administered in combination with cabiralizumab and nivolumab• To characterize the pharmacodynamic (PD) profile of APX005M when administered in combination with cabiralizumab and nivolumab• To further characterize the PD profile and immunogenicity of APX005M in combination with cabiralizumab and nivolumab by analyses of pre-treatment and on-treatment tumor biopsies and blood collection

Phase 1b Objectives

Primary

- Determine the objective response rate (ORR) using RECIST v1.1 to APX005M in combination with cabiralizumab and nivolumab in patients with advanced melanoma, non-small cell lung cancer (NSCLC), and renal cell carcinoma (RCC) whose tumors are resistant to anti-PD-1/PD-L1 therapy
- Evaluate the safety and tolerability of the RP2D of APX005M in combination with cabiralizumab and nivolumab

Secondary

- To determine the progression-free survival (PFS) of patients with melanoma, NSCLC or RCC treated with APX005M in combination with cabiralizumab and nivolumab whose tumors are resistant to anti-PD-1/PD-L1 therapy.
- To determine the overall survival (OS) of patients with melanoma, NSCLC or RCC treated with APX005M in combination with cabiralizumab and nivolumab whose tumors are resistant to anti-PD-1/PD-L1 therapy.

Exploratory

- To assess the association of selected biomarker measures and clinical efficacy measures using pre-treatment and on-treatment tumor biopsies
- To identify immune correlates that are associated with clinical response or resistance to the triple combination. Biomarker analyses will include study of pre-treatment and on-treatment biopsies as well as analyses of select serum and PBMC markers.

Investigational Products

- APX005M Solution for Intravenous Infusion
- Cabiralizumab Solution for Intravenous Infusion
- Nivolumab Solution for Intravenous Infusion

Study Design

This trial is a phase 1/1b study to evaluate the safety, efficacy, and tolerability of APX005M in combination with nivolumab and cabiralizumab. The phase 1 dose escalation portion will enroll patients with advanced solid tumors (melanoma, NSCLC, and RCC) to determine the RP2D of APX005M. The phase 1b dose expansion portion will study the triple drug combination in three disease cohorts. APX005M is a humanized IgG1 agonistic monoclonal antibody that binds CD40. Nivolumab is a humanized IgG4 monoclonal antibody directed against PD-1. Cabiralizumab is a humanized IgG4 monoclonal antibody directed against CSF1R.

[figure not shown]
Phase 1: Dose Escalation

Patients with advanced solid tumors will be sequentially enrolled in 6 cohorts using a standard 3 + 3 dose escalation design to determine safety, characterize the AEs, and establish the RP2D of APX005M in combination with nivolumab and cabiralizumab. A minimum of 48 hours observation will be required after each patient is enrolled in cohorts 1-6, before a subsequent patient can be enrolled. Approximately 3 patients will be enrolled per cohort. Cohorts 1, 3, and 5 will include cabiralizumab at 4 mg/kg and dose escalation of APX005M. Cohorts 2, 4, and 6 will include nivolumab at 240 mg, cabiralizumab at 4 mg/kg, and dose escalation of APX005M. Each cycle will be 14 days with anticipated dosing as follows:

Phase 1 Dose Escalation Cohorts

Cohort	Nivolumab (mg)	Cabiralizumab (mg/kg)	APX005M (mg/kg)
1	Not given	4	0.03
2	240	4	0.03
3	Not given	4	0.1
4	240	4	0.1
5	Not given	4	0.3
6	240	4	0.3

If none of the first 3 evaluable patients in a dose cohort experience a dose-limiting toxicity (DLT) in the first two cycles, then the next 3 patients will be treated at the next higher dose cohort. If 1 of 3 patients within a cohort experiences a DLT in the first two cycles, then 3 additional patients will be added to that cohort. If a second patient experiences a DLT at that dose level in the first two cycles, the next cohort will not be initiated, and the dose of one or more drugs will be de-escalated. Patients at each dose level will be evaluated for at least 4 weeks from the start of treatment before additional patients can be treated at a higher dose level. If DLTs are observed in 2 or more patients within a cohort, the maximum tolerated dose (MTD) will have been exceeded and no further patients will be treated at that dose level. At 8 weeks, imaging studies will be performed to assess for response. Of note, 2 sets of cohorts will be conducted simultaneously: Cohorts 2 and 3, and Cohorts 4 and 5, as depicted below.

Dose escalation will be based on the number of DLTs experienced during the DLT evaluation interval as determined by dose escalation meetings attended by the PIs and Industry Collaborators (see Section 3.1.2.1.1 for DLT criteria). The DLT evaluation interval begins on the first day of treatment and continues for 28 days.

Algorithm for Dose-Escalation Decisions

Number of Patients with DLT at a Given Dose Level	Dose Escalation Decision Rule
0/3	Escalation will occur into the next highest dose cohort
1/3	Enroll 3 additional patients at current dose level
≥2/3	Stop enrolment. Enroll 3 more patients at the lower dose level, if only 3 were previously entered, or at an intermediate dose level.
1/6	Open next cohort
≥2/6	Stop enrolment. Enter 3 more patients at the lower dose level or at an intermediate dose level.

Phase 1b Study

Once a specific dose regimen is determined to be safe as determined by the Sponsors and Industry Collaborators, the phase 1b portion will follow and will enroll additional patients in three disease-specific cohorts, all of whom who have progressed on prior PD-1/PD-L1 therapy: advanced melanoma, NSCLC,

and RCC who have progressed on prior PD-1/PD-L1 therapy. Patients will be treated at the estimated APX005M RP2D in combination with nivolumab 240 mg IV and cabirizumab 4 mg/kg on day 1 of each 14-day cycle.

Number of Patients

In the Phase 1 dose escalation portion, at least 3 patients with advanced solid tumors will be enrolled per cohort using a standard 3+3 design. There are a total of 6 cohorts. In the Phase 1b portion, a Simon's two-stage design will be used to study 3 disease cohorts: advanced melanoma, NSCLC, and RCC. The null hypothesis that the true response rate is 10% will be tested against a one-sided alternative. In the first stage, 13 patients in each disease cohort will be accrued. If there are 1 or fewer responses in these 13 patients, the enrollement in that disease cohort will be stopped. Otherwise, 21 additional patients will be accrued for a total of 34 patients per disease cohort. The null hypothesis will be rejected if 6 or more responses are observed in 34 patients. This design yield a type I error rate of 0.1 and a power of 80% when the true response rate is 25%.

Study Population

The phase 1 dose escalation portion will include patients with advanced melanoma, NSCLC, and RCC with the same criteria as listed below for the phase 1b portion.

The Phase 1b dose expansion portion of the trial studying APX005M at the RP2D in combination with cabirizumab and nivolumab will consist of three solid tumor cohorts. All patients in all tumor types are required to have progressed while on anti-PD(L)-1 therapy without any intervening therapy. Additional descriptions are below:

Melanoma:

- Unresectable stage III or stage IV melanoma, irrespective of *BRAF* status, with histologic or cytologic confirmation

RCC:

- Histologic or cytologically documented, locally advanced unresectable or metastatic RCC irrespective of histologic subtype

NSCLC:

- Histologic or cytologically documented, locally advanced or metastatic (i.e. Stage IIIB not eligible for definitive chemoradiotherapy, stage IV, or recurrent) NSCLC.
- Patients known to harbor an ALK rearrangement or EGFR mutation known to be sensitive to FDA-approved tyrosine kinase inhibitors (TKI), are only eligible after experiencing disease progression (during or after treatment) or intolerance to an FDA approved ALK TKI or EGFR TKI, respectively.
- Patients with TKI-treated EGFR mutant NSCLC harboring the secondary EGFR T790M tumor must have received prior osimertinib.
- Patients with crizotinib-treated ALK rearranged NSCLC must have received a next generation ALK inhibitor.

Inclusion Criteria

1. Biopsy proven metastatic melanoma, NSCLC or RCC whose disease has progressed on a prior regimen containing a PD-1 or PD-L1 inhibitor, without intervening therapy. Progression will be determined by the investigator based on clinical and/or radiographic features.
2. At least 1 site of disease must be accessible to provide repeat biopsies for tumor tissue. This site may be a target lesion as long as it will not be made unmeasurable by the biopsy procedure
3. Age ≥ 18 , able to understand and sign the informed consent form
4. ECOG performance status < 2
5. Any number of previous treatments. Other prior systemic therapies must have been administered at least 4 weeks before administration of the study drugs; the exception to this is small molecule inhibitors, which must be

stopped at least 2 weeks or after five half-lives of the drug, whichever is shorter, prior to the start of the study drugs.

6. Life expectancy of at least 6 months
7. A history of previously treated brain metastases is allowed, provided that they are stable for at least 4 weeks.
8. Willingness to undergo mandatory tumor biopsy prior to initiation of therapy and before the fifth cycle.
9. Willingness to provide an archival specimen block, if available, for research.
10. Patients must have normal organ and marrow function (as outlined in Section 3.2.2)
11. Female subject of childbearing potential should have a negative urine or serum pregnancy within 24 hours prior to receiving the first dose of study medication. If the urine test is positive or cannot be confirmed as negative, a serum pregnancy test will be required.
12. Female subjects of childbearing potential should be willing to use a highly effective contraception (hormonal or IUD) or be surgically sterile, or abstain from heterosexual activity for a period of at least 5 months after the last dose of study drug. Subjects of childbearing potential are those who have not been surgically sterilized or have not been free from menses for > 1 year.
13. Male subjects should agree to use an adequate method of contraception starting with the first dose of study therapy through at least 7 months after the last dose of study drug.
14. Patients must have at least one measurable lesion at baseline by computed tomography (CT) or magnetic resonance imaging (MRI) as per RECIST v1.1 criteria.
 - a. Tumor sites situated in a previously irradiated area, or in an area subjected to other loco-regional therapy, are not considered measurable unless there has been demonstrated progression in the lesion.
15. Prior focal radiotherapy is allowed. Radiation to brain, pulmonary or intestinal sites must be completed at least 4 weeks prior to study Day 1. There is no time restriction prior to study Day 1 for patients who have received radiation to bone, soft tissue or other sites. No radiopharmaceuticals (strontium, samarium) within 8 weeks before first dose of study drug administration.
16. Major surgery must be completed at least 4 weeks prior to the first dose of study drug administration. Surgery requiring local/epidural anesthesia must

be completed at least 72 hours before first dose of study drug administration and patients should have recovered. Wounds must be healed.

Exclusion Criteria

1. Untreated brain metastases.
2. A patient who has had prior immune therapy or chemotherapy, within 4 weeks prior to study Day 1, or who has not recovered (i.e., \leq Grade 1 or at baseline) from adverse events due to a previously administered agent will be excluded. The exception is targeted therapy that must have been completed at least 2 weeks or after 5 half-lives, which ever is shorter, prior to study Day 1. Patients who have had prior ipilimumab must have received their last dose no less than 4 weeks prior to study Day 1.
 - a. Note: If subject received major surgery, they must have recovered adequately from the toxicity and/or complications from the intervention prior to starting therapy.
 - b. Note: Toxicity that has not recovered to \leq Grade 1 is allowed if it meets the inclusion requirements for laboratory parameters.
3. Has had prior treatment with any other CSF1R inhibitor or CD40 agonist
4. Use of corticosteroids to control immune related adverse events at enrollment will not be allowed, and patients who previously required corticosteroids for symptom control must be off steroids for at least 2 weeks. Low-dose steroid use (\leq 10 mg of prednisone or equivalent) as corticosteroid replacement therapy for primary or secondary adrenal insufficiency is allowed.
5. Has not recovered (i.e., \leq Grade 1 or at baseline) from adverse events due to prior treatments with the exception of clinically insignificant adverse events such as alopecia, clinically insignificant laboratory abnormalities, clinically insignificant rash and Grade 2 neuropathy.
6. History of grade 3-4 neurologic or cardiac toxicity or life-threatening liver toxicity poorly responsive to steroids with prior anti-PD-1/anti-PDL1 monotherapy.
7. Presence of leptomeningeal disease.
8. Has active autoimmune disease unrelated to use of immune checkpoint inhibitors that has required systemic treatment in the past year (i.e. with use of disease modifying agents, corticosteroids or immunosuppressive drugs). Replacement therapy (eg., thyroxine, insulin, or physiologic corticosteroid replacement therapy for adrenal or pituitary insufficiency, etc.) is not considered a form of systemic treatment.
9. Pregnancy or breast feeding. Should a woman become pregnant or suspect she is pregnant while participating in this study, she should inform her treating physician immediately. Because there is an unknown but potential risk for adverse events in nursing infants secondary to treatment of the mother with nivolumab, cabiralizumab or APX005M, breastfeeding must be discontinued if the mother is enrolled on this trial.

10. Patients may not be receiving any other investigational agents and may not have participated in a study of an investigational agent or using an investigational device within 4 weeks of the first dose of treatment.
11. Either a concurrent condition (including medical illness, such as active infection requiring treatment with intravenous antibiotics or the presence of laboratory abnormalities) or history of a prior condition that places the patient at unacceptable risk if he/she were treated with the study drug or a medical condition that confounds the ability to interpret data from the study.
12. Concurrent, active malignancies in addition to those being studied.
13. Active (non-infectious) pneumonitis.
14. Has a known Human Immunodeficiency Virus (HIV), Hepatitis B (HBV), or Hepatitis C (HCV) acute or chronic infection.
15. Has received a live vaccine within 30 days prior to the first dose of trial treatment.
16. History of myocardial infarction or unstable angina within 3 months prior to Cycle 1, Day 1.
17. Prisoners, or subjects who are under compulsory detention
18. Current or history of clinically significant muscle disorders (e.g., myositis), recent unresolved muscle injury, or any condition known to elevate serum CK levels
19. History of anti-drug antibodies, severe allergic, anaphylactic, or other infusion-related reaction to a previous biologic agent
20. Concomitant use of statins while on study. However, a patient using statins for over 3 months prior to study drug administration and in stable status without CK rise may be permitted to enroll
21. Open wounds and active skin infections
22. Uveal melanoma in the Phase Ib dose expansion trial

Concomitant Medications	
All medications taken within 28 days before the administration of the first dose of any study drug and all concomitant therapy administered during the study until 100 (± 7) days after last dose of any study drug (or use of subsequent anti-cancer therapy) will be collected. All subsequent anti-cancer therapy will be collected in the Long-Term Follow-up Period.
 
Information on all prior treatments indicated for advanced cancer, including chemotherapy, biochemotherapy, immunotherapy, radiation, surgery, biologic, and experimental therapy will be collected.
 
No concomitant medication information will be collected following patient discontinuation from the study except for concomitant medication use associated with study drug-related AEs or AEs that lead to discontinuation from the study.

Withdrawal Criteria	
Patients must discontinue study drugs for any of the following reasons:
 
• Withdrawal of informed consent (patient's decision to withdraw for any reason)• Any clinically significant AE, abnormal laboratory test results, or intercurrent illness which, in the opinion of the Investigator, indicates that continued participation in the study is not in the best interest of the patient• Patients who are required to have prohibited concomitant medications• Pregnancy• Termination of the study by the Sponsor• Loss of ability to freely provide consent through imprisonment or involuntary incarceration for treatment of a psychiatric or physical (e.g., infectious disease) illness• Documented disease progression or clinical deterioration while receiving active study therapy• Non-compliance by the patient

List of Key Study Personnel

Sponsor:	Yale Cancer Center
Industry Collaborators:	Bristol-Myers Squibb, Apexigen, Inc.
Principal Investigator:	[name]
Co-Principal Investigators:	[name]
	[name]
Co-Investigators:	[name]
	[name], PhD
	[name], PhD
	[name]
Serious Adverse Event Reporting:	Bristol-Myers Squibb
	Apexigen, Inc.
	FDA

Table of Contents

Study Synopsis.....	2
List of Key Study Personnel	13
Table of Contents.....	14
List of Abbreviations and Definitions.....	20

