1.3.6 Clinical Summary

1.3.6.1 Cabiralizumab

1.3.6.1.1 Clinical Study Summary of Cabiralizumab

The clinical summary is based on three clinical studies:

1. Study FPA008-001 evaluated the safety of cabiralizumab as single or dual escalating doses in 48 healthy volunteers (36 cabiralizumab and 12 placebo). This study also evaluated the safety and efficacy of cabiralizumab administered as two or three doses, 14 days apart, in 18 rheumatoid arthritis patients. This study has been completed.
2. Study FPA008-002 is evaluating the safety and efficacy of cabiralizumab monotherapy for six months in approximately 40 patients with pigmented villonodular synovitis (PVNS).
3. Study FPA008-003 is evaluating the safety and efficacy of cabiralizumab as monotherapy and in combination with nivolumab in approximately 295 patients with advanced cancers.

1.3.6.1.2 Clinical Pharmacology Summary (Pharmacokinetics, Immunogenicity, and Pharmacodynamics) of Cabiralizumab

The available PK, ADA, and nonclassical CD16⁺ monocyte status following cabiralizumab treatment with either monotherapy or in combination with nivolumab were characterized in three trials: FPA008 001, FPA008-002, and FPA008-003. The PK, ADA, and nonclassical CD16⁺ monocyte data from Study FPA008-003 are summarized below; data from Studies FPA008 001 and FPA008-002 are presented in the cabiralizumab IB.

The PK profile of cabiralizumab is characterized by linear and nonlinear clearance pathways, with the latter likely mediated by binding to CSF1R on cells. As monocyte and macrophage cells are dependent on CSF1R for viability, these target-bearing cells are reduced in number following cabiralizumab treatment, resulting in a decrease of target-mediated clearance. Once target mediated clearance is saturated at high or repeat doses, cabiralizumab clearance is similar to other human IgG antibodies.

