4.3 Method of Assigning Patient Identification

Patients must be able to provide written informed consent and meet all eligibility criteria. No waivers of inclusion or exclusion criteria will be granted by Sponsor or its designee for any patient enrolled in the study. Before enrolling a patient, all eligibility criteria must be satisfied.

See Section 4.4.1 and Figure 6 for dosing schema. Patients who qualify for Phase 1 dose escalation of the study will be enrolled as follows:

- Cohort 1 will be enrolled first and these patients will be followed one 14-day cycle.
- Once the DLT follow-up period of 28 days is cleared for Cohort 1, simultaneous enrollment to Cohort 2 and Cohort 3 will occur. Patients in these cohorts will be treated for a total of one 14-day cycle.
- Simultaneous enrollment into Cohort 4 and Cohort 5 will proceed once the 14-day DLT

period for dose escalation is cleared in the preceeding Cohorts 2 and 3.

- Once the DLT period of 28 days for dose escalation is cleared Cohorts 4 and 5, enrollment to the final Cohort 6 will occur.
- The MTD will be calculated for patients who have received at least 2 cycles (at least 28 days) of study drug.
- Dose escalation into sequential dose levels of APX005M in combination with cabiralizumab and nivolumab may proceed until DLTs are observed either in the cabiralizumab/APX005M doublet therapy cohorts 1, 3, and 5 or in the nivolumab/cabiralizumab/APX005M triplet therapy cohorts after discussion and agreement between the PIs and Industry Collaborators.

In Phase 1b, a maximum of 34 patients will be enrolled per disease-specific cohort (advanced melanoma, NSCLC, or RCC). Enrollment will be open for all cohorts in parallel and will continue until the enrollment target is reached. Once a disease cohort is filled, further enrollment will be restricted to the cohort(s) that have not been filled. A total of approximately 102 patients will be enrolled in the Phase 1b arm of the study.

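### Exclusion 3 does not clearly bar prior cabiralizumab or APX005M, so on a literal reading a patient who progressed on cabiralizumab plus nivolumab can enter the response test

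*Combined protocol and SAP*

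**What the plan says.** Criterion 3 of the exclusion list excludes a patient who "Has had prior treatment with any other CSF1R inhibitor or CD40 agonist". The wording is the same in the Study Synopsis and in Section 3.2.3, which applies to all cohorts. Neither list names cabiralizumab or APX005M as barred prior treatment.

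The neighbouring criteria are:

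- Inclusion 1 (synopsis) takes patients "whose disease has progressed on a prior regimen containing a PD-1 or PD-L1 inhibitor, without intervening therapy". Section 3.2.2 has the same requirement in similar words.
- Inclusion 5 sets no limit on the number of earlier treatments.
- Exclusion 2 removes "A patient who has had prior immune therapy or chemotherapy, within 4 weeks prior to study Day 1".
- Exclusion 10 says "Patients may not be receiving any other investigational agents" and that they "may not have participated in a study of an investigational agent or using an investigational device within 4 weeks" of the first dose.
- Exclusion 19 removes patients with "History of anti-drug antibodies, severe allergic, anaphylactic, or other infusion-related reaction to a previous biologic agent".

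Section 4.3 adds that "No waivers of inclusion or exclusion criteria will be granted by Sponsor or its designee". Section 1.3.6.1.1 describes the main source of earlier exposure: "Study FPA008-003 is evaluating the safety and efficacy of cabiralizumab as monotherapy and in combination with nivolumab in approximately 295 patients with advanced cancers".

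**The concern.** The phase 1b test asks whether adding CSF1R inhibition and CD40 agonism to PD-1 blockade produces responses in tumours resistant to PD-1/PD-L1 therapy. A patient who progressed on cabiralizumab plus nivolumab has already failed two of those three components. For that patient the trial tests only the addition of APX005M, which is a different question.

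If such patients respond less often, they lower the observed response rate and make it more likely that a disease cohort stops after 13 patients or misses the final threshold. The eligibility list should settle whether they belong in the test, and it does not.

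**Working it through.** **Step 1. What the wording admits.** Take a patient with melanoma, NSCLC or RCC whose last regimen was cabiralizumab plus nivolumab, who progressed on it, and who is more than 4 weeks from the last dose.

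- Inclusion 1: met. The regimen contained a PD-1 inhibitor and nothing intervened.
- Exclusion 2: not triggered after 4 weeks, provided earlier toxicity has recovered.
- Exclusion 3: turns on *other*. Exclusion 10, in the same list, uses *other* for agents apart from the study drugs. Read the same way, exclusion 3 leaves cabiralizumab and APX005M out of the ban.
- Exclusion 10: not triggered after 4 weeks.
- Exclusion 19: triggered only by known anti-drug antibodies or a past reaction.

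With no waivers granted, the list is applied as written, and nothing in it clearly removes this patient.

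**Step 2. The plan's own design figures.** Section 7.1 gives 13 patients in stage 1, stopping at 1 or fewer responses; 21 more, for 34 in total; rejection at 6 or more responses; null rate 10%, alternative 25%; type I error 0.1 and power 80%.

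The exact probability of rejection is the sum over x = 2 to 13 of P[Bin(13, p) = x] × P[Bin(21, p) ≥ 6 − x].

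At p = 0.25:

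- x = 2: 0.2059 × 0.8083 = 0.1664
- x = 3: 0.2517 × 0.9255 = 0.2329
- x = 4: 0.2097 × 0.9810 = 0.2057
- x = 5: 0.1258 × 0.9976 = 0.1255
- x ≥ 6: 0.0802 × 1 = 0.0802

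The total is 0.811. At p = 0.10 the same sum gives 0.0957. Both stated figures are met.

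**Step 3. Adding pre-exposed patients.** Let m1 of the 13 and m2 of the 21 be pre-exposed, with response rate q. Stage 1 responses become Bin(13 − m1, 0.25) + Bin(m1, q), stage 2 responses become Bin(21 − m2, 0.25) + Bin(m2, q), and the decision rule is unchanged. The values of m1, m2 and q are assumptions; the documents supply none of them.

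| Pre-exposed (stage 1, stage 2) | Power, q = 0% | Power, q = 10% |
|---|---|---|
| 0, 0 | 0.8108 | 0.8108 |
| 0, 1 | 0.7985 | 0.8034 |
| 1, 0 | 0.7739 | 0.7887 |
| 1, 1 | 0.7607 | 0.7810 |
| 2, 2 | 0.7006 | 0.7475 |

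Placement matters because of the early stop. With 25% in the other patients and q = 0%, the chance of stopping after 13 is 0.127 with no pre-exposed patient in stage 1, 0.158 with one and 0.197 with two. The extreme case of all four in stage 1 gives power of 0.6224 (q = 0%) to 0.7080 (q = 10%). If four were spread at random over the 34 places, that would happen with probability C(13,4)/C(34,4) = 715/46,376, or about 1.5%.

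**Step 4. Type I error.** With the other patients at 10%, type I error stays at 0.0957 if q = 10%. If q = 0% it falls to 0.075 with one pre-exposed patient per stage and to 0.057 with two per stage.

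**The case against.** The strongest reply is that *any other* is loose drafting and the authors meant to bar both drug classes. That is possible, and it means eligibility cannot be stated as a fact. It does not remove the point: the text does not say which was meant, and the same edit settles it either way.

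Second, the route is narrow. The no-intervening-therapy condition already removes patients whose cabiralizumab or APX005M monotherapy followed PD-1 progression. The 295 patients in the earlier cabiralizumab study cover monotherapy and combination across advanced cancers; the number with these three tumours, or within reach of this single institution, is not given. This stands, and it limits the size of the problem.

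Third, a 0% response is a worst case. The rationale in Section 1.2 is that combining the agents may overcome resistance, so these patients need not be certain non-responders. This also stands, and it is why the results are shown as a range.

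Fourth, Section 3.3 records prior immunotherapy, biologic and experimental treatment, so pre-exposed patients could be identified at analysis. That helps interpretation but does not undo a stage 1 stop.

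A reader might also infer that phase 1 patients who progressed on this trial's own triplet at a lower APX005M dose could be screened again for phase 1b. The documents do not support that. The synopsis says phase 1b enrols additional patients, and the only stated route from phase 1 into the two-stage test is exposure at the MTD (Section 7.1). Patients come off drug at documented progression, or at further progression if treated beyond it (Sections 4.11 and 4.13), and then enter follow-up (Section 5.2.3). Phase 1 doublet patients received no PD-1 drug, so the doublet would itself be an intervening therapy. Nor could re-entry into phase 1b distort the DLT counts, which drive phase 1 escalation.

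**Conclusion.** The gap in the wording is real and bears on who belongs in the primary efficacy test. Read literally, exclusion 3 leaves prior cabiralizumab and APX005M unbarred, and the practical case is progression on cabiralizumab plus nivolumab as the last regimen.

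The size is uncertain and probably modest. For one to four pre-exposed patients of 34, no more than two in either stage, power runs from about 0.80 (one patient, in stage 2) to 0.70 (two per stage, 0% response). With only one or two, split as in the table, it is about 0.76 to 0.80. These figures rest on assumed numbers, an assumed response rate of 0% to 10% in those patients, and 25% in the rest. The harm would be lost power and a mixed population. A reader might infer a greater risk of a false positive; the calculation shows none while pre-exposed patients respond at 10% or less.

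**What to change.** In exclusion 3, in the synopsis and in Section 3.2.3, delete the word *other* and add at the end: *including cabiralizumab and APX005M*. If the sponsor does want pre-exposed patients, the plan should say so and report their responses separately.

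Optionally, add one sentence confirming that the MTD carry-over in Section 7.1 is the only route from phase 1 into the two-stage test. This would also make clear that carried-over patients, who are counted on their original course, are not caught by the revised criterion.

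The cost is one word deleted and a short phrase added in two places. At most a few patients become ineligible. The sample sizes, thresholds, exact type I error (0.0957) and exact power (0.811) are unchanged.
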